10.4.4. Safety Analyses

For the safety analysis, data from all subjects from the safety analysis population will be included. All analyses will be descriptive. Data will be presented by dose, overall/dose and overall/subject. Results

will be summarized by study group. The percentage of subjects with at least one AE during the follow-up period will be tabulated with exact 95% CI (two-sided). No multiplicity adjustment will be implemented in analysis. The reports of solicited and unsolicited AEs will be reviewed by a physician and will be categorized by the MedDRA dictionary. The percentage of subjects with at least one report of unsolicited AE and reported up to 28 days after each anti-malarial course will be tabulated with exact 95% CI. The percentage of subjects with at least one report of unsolicited AE and reported up to 28 days after each vaccine dose will be tabulated with exact 95% CI.

The occurrence of SAEs will be determined on the safety analysis population. The proportion of subjects with an SAE, classified by the MedDRA preferred term level, reported from study start until study conclusion will be tabulated with exact 95% CI. Comparisons between groups will be done using Fisher's Exact Test for each preferred term. Serious adverse events (SAEs) occurring at any point during the trial will be summarized and relatedness to vaccine will be assessed.

Withdrawals due to AEs/SAEs will also be summarized. Vital signs which are outside of the normal range and clinically significant will also be listed in tables. The frequency of signs and symptoms will be compared between groups with the chi-square test or Fisher's exact test.

The occurrence of Grade 3 solicited and unsolicited general reactions will be determined on the Total Vaccinated Cohort. The proportion of subjects with a Grade 3 solicited and unsolicited reaction, reported from study start until study conclusion will be tabulated with exact 95% CI. Comparisons between groups will be done using Fisher's Exact Test.

The occurrence of adverse events will be determined on the Total Vaccinated Cohort. The proportion of subjects with an AE, classified by the MedDRA preferred term level, reported from study start until study conclusion will be tabulated with exact 95% CI. Comparisons between groups will be done using Fisher's Exact Test.

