	
Safety:
 
 • Frequency count and proportion of subjects reporting serious adverse events (SAEs) during the whole study period (from Dose 1 to study conclusion) • Frequency count and proportion of subjects reporting solicited local and systemic adverse events within 7 days after each vaccination • Frequency count and proportion of subjects reporting unsolicited adverse events within 28 days after each vaccination 
Immunogenicity:
 
 • Anti-circumsporozoite (CS) antibody levels & avidity and hepatitis B surface antibody (HBsAb) antibodies from subjects in Groups 1, 2, and 3 at time points indicated in Appendix F as measured by ELISA assays. 
Exploratory Endpoints:
 
 • Anti-rabies antibodies at timepoints indicated in Appendix F in subset of subjects in Groups 4 and 5. • Cell-mediated immune responses in subjects administered RTS,S/AS01_E (Groups 1, 2, and 3) will be descriptive in nature. • RNA transcriptional responses for all subjects in Groups 1 – 5. • HLA typing in subjects administered RTS,S/AS01_E (Groups 1, 2, and 3). • Cross-sectional malaria PCR/DBS at Study Termination visit in Groups 1 – 5. 
Note: additional immunological assays evaluating the immune response to CS and HBsAg might be performed.

Population	Adults 18 to 55 years old at enrollment, inclusive.
Phase	Phase 2b
Number of sites enrolling participants	One site; Kombewa Clinical Research Center, Kenya
Description of study agent	
 • RTS,S/AS01_E vaccine 0.5mL, containing 25 µg RTS,S, 25 µg MPLs, 25 µg QS21 in a liposomal formulation) for the first two immunizations. One-fifth dose RTS,S/AS01_E vaccine for third immunization. • Comparator Abhayrab rabies vaccine (one dose, 0.5 mL, contains 2.5 IU rabies antigen). • Dihydroartemisinin-piperaquine (DHA/Pip) is a long acting anti-malarial. • Coartem®(artemether/lumefantrine); Coartem is a short-acting ACT that is used in this study to provide clearance of blood stage parasites before assessment of vaccine efficacy. It is used in this study to remove any confounding anti-malarial effects when analyzing time to infection and vaccine efficacy. • Primaquine; Low dose Primaquine (LD PQ) is an 8-aminoquinoline that clears stage 5 gametocytes of P. falciparum.

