3. OBJECTIVES AND PURPOSE

Primary Objective:

To assess vaccine efficacy assessed by time to first *P. falciparum* infection in RTS,S/AS01_E vaccinated adults (Group 1) positive for *P. falciparum* by PCR at baseline and treated to clear parasites compared to adults administered a comparator vaccine (Group 4) positive for *P. falciparum* by PCR at baseline and treated to clear parasites.

Secondary Objectives:

Efficacy:

To assess vaccine efficacy by time to first *P. falciparum* infection by PCR in RTS,S/AS01_E vaccinated adults (Group 2) negative for *P. falciparum* at baseline and provided anti-malarial chemo-prophylaxis versus comparator group (Group 5) negative for *P. falciparum* at baseline and provided anti-malarial chemo-prophylaxis.

Safety:

- To assess the safety of RTS,S/AS01_E in terms of serious adverse events (SAEs) during the whole study period (from Dose 1 to study conclusion)
- To assess the safety and reactogenicity of RTS,S/AS01_E in terms solicited local and systemic adverse events within 7 days after each vaccination in the first 50 subjects in groups 1 and 2, and in all 35 subjects from Group 3.
- To assess the safety of RTS,S/AS01_E in terms of unsolicited adverse events within 28 days after each vaccination

Immunogenicity:

- To assess anti-circumsporozoite (CS) antibody levels & avidity, hepatitis B surface antibodies (HBsAb), from groups 1, 2 and 3 as detailed in Appendix F.

Exploratory Objectives:

- To assess in subjects immunized with RTS,S/AS01_E the relationship between HLA Class 1 and Class 2 alleles with protection against *P. falciparum* infection.
- To assess anti-rabies antibodies in subset of subjects at time points from groups 4 and 5 as shown in Appendix F.
- To assess cell-mediated immune responses and transcriptomes in Groups 1 – 3.
- Other immunological assays evaluating the immune response to CS and HBsAg might be performed.
- To assess malaria cross-sectional prevalence in all study participants at the end of the study.

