4.2.2. Secondary Endpoints

Secondary endpoint for vaccine efficacy:

The secondary endpoint is defined as the time to first PCR-positive malaria infection in Groups 2 and 5 during the ADI phase of the study. Vaccine efficacy in African adults administered RTS,S, and who are negative for *P. falciparum* infection at baseline and given anti-malaria chemoprophylaxis (Group 2) are compared to rabies vaccinated adult subjects who are negative for *P. falciparum* infection at baseline and given anti-malaria chemoprophylaxis (Group 5).

Secondary endpoint for safety:

- Frequency count and proportion of subjects reporting serious adverse events (SAEs) during the whole study period
- Frequency count and proportion of subjects reporting solicited local and systemic adverse events within 7 days after each vaccination
- Frequency count and proportion of subjects reporting unsolicited adverse events within 28 days after each vaccination

Secondary endpoint for immunogenicity:

- Anti-circumsporozoite (CS) antibody levels & avidity at time points shown in Appendix F.
- Hepatitis B surface antibody (HBsAb) levels at time points shown in Appendix F.

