8.3. Time Period and Frequency of Event Assessment and Follow-up

All solicited local and systemic AEs occurring within 7 days following administration of each dose of vaccine must be recorded on the CRF for the first 50 subjects in groups 1 and 2 and from all subjects in group 3 (Reactogenicity Cohort). All subjects being followed for solicited AEs will be offered a memory aid to assist in recall of AEs. All unsolicited AEs occurring within 28 days following administration of each dose of vaccine and, where applicable, course of per protocol scheduled anti-malarial treatment, must be recorded on the CRF for all subjects. All SAEs that occur will be collected and recorded from the time the subject consents to participate in the study until she/he is discharged. The occurrence of an AE or SAE may come to the attention of study personnel during study visits and field worker visits. Information to be collected includes event description, date of onset, clinician's assessment of severity, relationship to study product, and date of resolution/stabilization of the event. All AEs occurring while on study must be documented appropriately regardless of relationship. All AEs will be followed to adequate resolution.

Any medical condition that is present at the time that the participant is screened will be considered as baseline and not reported as an AE. However, if the study participant's condition deteriorates at any time during the study, it will be recorded as an AE.

After the initial AE/SAE report, the investigator is required to proactively follow each subject and provide further information per study reporting procedures (section 8.4). All AEs and SAEs documented at a previous visit/contact and designated as not recovered/not resolved or recovering/resolving will be followed-up.

Investigators will follow-up subjects:

- with SAEs or who are withdrawn from the study as a result of an AE, until the event has resolved, subsided, stabilized, disappeared, the event is otherwise explained, or the subject is lost to follow-up;
- or, in the case of other non-serious AEs, until the AE resolves, they complete the study, or they are lost to follow-up.

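### Section 10.4.4 counts SAEs and AEs from an undefined study start, while the SAE objective and synopsis endpoint run from Dose 1 (minor)

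*Protocol*

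**What the plan says.** All references are to the protocol.

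- **Synopsis, secondary safety endpoints:** "Frequency count and proportion of subjects reporting serious adverse events (SAEs) during the whole study period (from Dose 1 to study conclusion". The section 3 objective has the same start: "serious adverse events (SAEs) during the whole study period (from Dose 1 to study conclusion".
- **Section 4.2.2:** "Frequency count and proportion of subjects reporting serious adverse events (SAEs) during the whole study period", with no start point.
- **Section 8.3, collection:** "All SAEs that occur will be collected and recorded from the time the subject consents to participate in the study until she/he is discharged".
- **Section 10.4.4, SAE analysis:** "The proportion of subjects with an SAE, classified by the MedDRA preferred term level, reported from study start until study conclusion", with an exact 95% CI and a Fisher test for each preferred term.
- **Section 10.4.4, AE analysis:** "The proportion of subjects with an AE, classified by the MedDRA preferred term level, reported from study start until study conclusion", again with Fisher tests between groups. Grade 3 solicited and unsolicited reactions get the same window and test.
- **Unsolicited AE endpoint, section 4.2.2:** "Frequency count and proportion of subjects reporting unsolicited adverse events within 28 days after each vaccination". Section 10.4.4 has a table for this window, and another for the 28 days after each antimalarial course. Both are tabulations with exact CIs.

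The phrase *study start* is not defined. Screening falls on days -39 to -28. Visit 2, with randomisation and the first antimalarial course in Groups 1, 2, 4 and 5, is on day -27, and AE recording begins at that visit (section 7.1.1, Appendix B). Dose 1 is on day 1.

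**The concern.** A vaccine cannot cause an event that precedes it. If the analysis window opens before Dose 1, two things follow for subjects who are later vaccinated. An SAE on day -10 in a Group 1 subject counts as an RTS,S-group SAE in section 10.4.4, although it lies outside the synopsis endpoint. A headache on day -26, after the first antimalarial dose, already makes the subject a case for that preferred term, so a headache after vaccination adds nothing to the proportion. The overlap of terms is real: section 2.3.1 lists headache for both the vaccines and DHA/Pip, and abdominal pain, nausea and vomiting for both the vaccines and primaquine.

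At stake are whether the SAE endpoint is reported as the synopsis defines it, and how far the vaccine comparisons are diluted by events that no vaccine could have caused.

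**Working it through.** The plan states no SAE or AE rate and no safety power, so there is no figure of its own to reproduce. The day counts below come from the schedule. Every event rate and effect size is an assumption.

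**1. What *study start* can mean.** Section 7.1.1 places a community information programme before study start, so there the phrase means a point before recruitment, not a subject's Dose 1. Section 10.4.4 also summarises SAEs at any point in the trial. On the other side, the synopsis explains the whole study period as Dose 1 to conclusion. The earlier start is the likelier reading but not the only one.

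**2. SAE time before Dose 1.** Day -27 to day 0 is 28 days. Day -39 to day 0 is 40 days.
- To Visit 27 (day 372): 28/(28+372) = 7.0%; 40/(40+372) = 9.7%.
- To Visit 35 (day 540): 28/(28+540) = 4.9%; 40/(40+540) = 6.9%.

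**3. SAE dilution.** Let p be the rabies-group risk over 372 days after Dose 1 and RR the true risk ratio. The pre-dose risk over d days is the same in both groups: q = 1 − (1−p)^(d/372). The observed risks are 1 − (1−p)(1−q) and 1 − (1−RR·p)(1−q). With p = 5%, RR = 2, and 164 per group:

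| Window | q | Rabies v RTS,S | Risk ratio | Risk difference | Fisher power (two-sided 5%) |
|---|---|---|---|---|---|
| From Dose 1 | 0 | 5.00% v 10.00% | 2.00 | 5.0 points | 32.5% |
| Plus 28 days | 0.39% | 5.37% v 10.35% | 1.93 | 5.0 points | 31.0% |
| Plus 40 days | 0.55% | 5.52% v 10.50% | 1.90 | 5.0 points | 30.4% |

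For p from 1% to 10% the diluted risk ratio stays at about 1.90–1.93.

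**4. AE capture days, Groups 1, 2, 4 and 5.** Capture runs 28 days from each antimalarial course (days -27, 15, 190) and each vaccine dose (days 1, 29, 197). The union is days -27 to 56 and 190 to 224, which is 84 + 35 = 119 days. Of these, 28 precede Dose 1: 28/119 = 23.5%. Counting both ends of each window gives 28/121 = 23.1%.

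**5. AE dilution for one preferred term.** Let b be the assumed background risk per 28 days, with daily hazard h = −ln(1−b)/28, doubled after vaccination. There are 119 − 28 = 91 capture days from Dose 1. The risks from Dose 1 are 1 − exp(−91h) and 1 − exp(−182h). Starting earlier adds 28h to both exponents, or 84h if the first antimalarial course triples the rate. At 164 per group:

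| b | Window | Rabies v RTS,S | Risk ratio | Risk difference | Fisher power |
|---|---|---|---|---|---|
| 4% | From Dose 1 | 12.4% v 23.3% | 1.88 | 10.9 points | 69% |
| 4% | From day -27 | 15.9% v 26.4% | 1.66 | 10.5 points | 60% |
| 4% | From day -27, tripled | 22.5% v 32.1% | 1.43 | 9.6 points | 45% |
| 1% | From Dose 1 | 3.2% v 6.3% | 1.97 | 3.1 points | 17.8% |
| 1% | From day -27 | 4.2% v 7.3% | 1.74 | 3.1 points | 15.6% |

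**6. Group 3.** It receives no antimalarials, so its AE windows follow the vaccine doses only: 3 × 28 = 84 days, none before Dose 1, against 119 days in the other groups. If the tested AEs are limited to 28 days after a vaccine dose, every group has the same 84 days.

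**The case against.** The case for leaving this alone is substantial.

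- **Section 4.2.2 gives no Dose 1 start**, so section 10.4.4 does not contradict it. This stands. The conflict is with the synopsis and section 3.
- **The SAE dilution is close to negligible.** This stands: about 2 points of power and almost no change in the risk difference.
- **The AE endpoint already has its own table.** This stands. A reader might infer that the 28-day AE endpoint goes unanalysed, and it does not. But the Fisher comparisons by preferred term and for Grade 3 reactions are attached to the longer window. A further sentence compares signs and symptoms between groups and states no window.
- **There is no directional bias in the randomised pairs.** This stands. A reader might infer that the window favours RTS,S or hides a safety signal. Groups 1 and 4, and Groups 2 and 5, are randomised and receive the same antimalarials, so the added events are noise of equal expected size. The larger power losses appear only for common terms under assumed rates, and the tripling has no source in the documents.
- **The analyses are called descriptive, unvaccinated subjects are excluded, and relatedness is judged event by event.** All true, and this limits the consequence. The exclusion does not remove pre-dose events of subjects who are later vaccinated.
- **Windows are ordinary SAP work.** In general yes, but here the protocol itself fixes a window that conflicts with its own synopsis.

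**Conclusion.** The inconsistency is real and minor. The SAE objective and synopsis endpoint start at Dose 1, while the only specified SAE proportion and test start at an undefined point that most naturally lies before it. For SAEs the consequence is that the endpoint is not analysed as the synopsis defines it. The dilution is small: 7–10% of the time to day 372, and a risk ratio of 2 seen as about 1.9, assuming a constant rate that is equal in both groups before Dose 1.

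For the added AE comparisons by preferred term, about 24% of capture days precede Dose 1 in Groups 1, 2, 4 and 5. A risk ratio near 2 could then show as about 1.7, or about 1.4 to 1.5 if the first antimalarial course triples the rate. Those ratios rest wholly on assumed rates, and risk differences move little. AE comparisons with Group 3 are different in kind, because its capture window is shorter and opens only at Dose 1.

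**What to change.** In section 10.4.4, run the SAE endpoint and all between-group vaccine comparisons on events with onset on or after Dose 1, and limit the compared unsolicited AEs to onset within 28 days after a vaccine dose. Report events from consent to Dose 1 in a separate table. Give section 4.2.2 the same SAE start as the synopsis and section 3, and define *study start* or drop it. Collection from consent under section 8.3 need not change.

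The cost is a wording change in two sections, carried into the SAP, and one extra table. Section 8.3 already requires the onset date of each event, so no new data are needed.

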10.5.1. Randomization Procedures

Eligible subjects will be randomized to their assigned group with secure IWRS (or in the absence of web connectivity, IVRS), which will be developed and managed by the PATH designated CRO. The IWRS/IVRS allows authorized staff from the study site to perform subject randomization and treatment assignment 24 hours a day, 7 days a week.

Subjects will be stratified by baseline parasitemia status and then block randomized. Among those positive for parasitemia at baseline a total of 363 will be randomized. The first 105 will be randomized in a 1:1:1 ratio with 35 subjects assigned to each of Groups 1, 3 and 4. The next 258 subjects with baseline parasitemia will be randomized in a 1:1 ratio to Groups 1 and 4 with a total of 129 additional subjects per group. Two hundred fifty-six subjects that are negative for parasitemia at baseline will be randomized with a 1:1 ratio to Groups 2 and 5. This randomization schedule will result in a total of 164, 128, 35, 164, and 128 for Groups 1 through 5, respectively. Additional details of the randomization procedure, such as block size, will be described in the Randomization Plan. HIV infection status will be noted prior to randomization, and individuals will be stratified across the groups to the extent possible. The proportion of subjects per group that are HIV positive will be capped near 20-25% for each group.

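### Safety tests are ordered between unspecified study groups, with no stratified RTS,S versus rabies contrast, although the objective is the safety of RTS,S and a randomised 292 v 292 comparison is available

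*Protocol*

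**What the plan says.** **Objective.** Protocol section 3 sets out to assess the safety of RTS,S/AS01E "in terms of serious adverse events (SAEs) during the whole study period (from Dose 1 to study conclusion"), together with solicited and unsolicited adverse events (AEs). The object of interest is the vaccine.

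**Analysis.** Section 10.4.4 says that results "will be summarized by study group". For SAEs it adds: "Comparisons between groups will be done using Fisher's Exact Test for each preferred term". Fisher comparisons between groups are repeated for Grade 3 reactions and for AEs, and signs and symptoms are compared by chi-square or Fisher. The same section says "All analyses will be descriptive" and "No multiplicity adjustment will be implemented in analysis". It does not list which groups are compared, and it contains no pooled vaccine contrast and no stratification.

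**Randomisation.** Section 10.5.1 says: "Subjects will be stratified by baseline parasitemia status and then block randomized". In the positive stratum, "The first 105 will be randomized in a 1:1:1 ratio with 35 subjects assigned to each of Groups 1, 3 and 4", and then "The next 258 subjects with baseline parasitemia will be randomized in a 1:1 ratio to Groups 1 and 4". The 256 parasite-negative subjects go 1:1 to Groups 2 and 5.

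**Treatment.** Tables 1 and 2 give Groups 1, 2, 4 and 5 the same antimalarial schedule. Group 3 receives RTS,S without scheduled antimalarials.

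**The concern.** The unit of the safety comparison does not match the objective. A study group here combines baseline infection status, vaccine and, for Group 3, absence of antimalarials. A comparison between groups answers a question about RTS,S only when the two groups differ in vaccine alone. Two pairs meet that condition, and each uses only one stratum.

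Two things are at stake. First, if the tests are confined to those two pairs, an imbalance that runs the same way in both strata is never tested on all the randomised subjects who bear on it. Second, if the tests are run across all five groups or over all pairs, a difference between parasitaemic and non-parasitaemic adults, or between treated and untreated adults, can produce a small p-value that has nothing to do with the vaccine.

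**Working it through.** **1. Allocation (section 10.5.1).** Groups 1 and 4: 35 + 129 = 164 each. Groups 2 and 5: 256 / 2 = 128 each. Group 3: 35. Total: 105 + 258 + 256 = 619. These match the protocol's figures.

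**2. Pairs.** Five groups give 10 pairs.
- Six cross the strata and are not randomised comparisons: 1-2, 1-5, 2-3, 2-4, 3-5, 4-5.
- Four lie within a stratum: 1-3, 1-4, 3-4, 2-5.
- Of these four, 1-3 differs in antimalarials and 3-4 differs in both vaccine and antimalarials. Both were randomised concurrently only in the first 105 positive subjects.
- That leaves 1-4 (164 v 164) and 2-5 (128 v 128) as vaccine contrasts.

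**3. Available pooled contrast.** RTS,S (Groups 1+2) v rabies (Groups 4+5): 164 + 128 = 292 per arm, 1:1 within each stratum. Group 3 does not belong in it, because no rabies group goes without antimalarials.

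**4. Smallest detectable split.** Two-sided Fisher p-values against zero events, for 128 to 292 per arm: 5 v 0 gives 0.060 to 0.061, and 6 v 0 gives 0.029 to 0.031. At all three sizes at least six events to none are needed. Pooling makes such a count more likely to be reached.

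**5. Exact power.** Two-sided Fisher at 0.05, enumerated over binomial outcomes. All event rates are assumptions.

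| RTS,S v rabies | 128 per arm | 164 per arm | 292 per arm |
|---|---|---|---|
| 6% v 2% | 25% | 34% | 65% |
| 5% v 1% | 31% | 45% | 78% |
| 3% v 0% | 19% | 37% | 87% |
| 2% v 0.5% | 2.5% | 5.6% | 22% |
| 1% v 0% | 0.2% | 0.6% | 7.5% |

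The last column is pooled Fisher. Direct enumeration of the stratified exact test gives the same values to the precision shown. The 3% row corresponds to about 292 x 0.03 = 8.8 subjects with the event against none.

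**6. Two illustrative outcomes, Groups 1 to 5 in order.**
- Events 3, 3, 0, 0, 0, a consistent vaccine imbalance: p = 0.25 for 1 v 4, p = 0.25 for 2 v 5, and p = 0.14 for a five-group Fisher test. The stratified exact test of RTS,S v rabies gives p = 0.031.
- Events 0, 4, 0, 0, 4, no vaccine difference: a five-group Fisher test gives p = 0.011. The stratified test gives p = 1, since the vaccines are level at 4 v 4.

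**The case against.** **No pairs are named.** A reader might infer that the six cross-stratum pairs will be tested. The text does not say so. It lists neither pairs nor an omnibus test, and it would also fit 1 v 4 and 2 v 5, the only contrasts the protocol names for testing (sections 10.2, 10.4.2 and 10.4.3). The pair count shows what an all-pairs or omnibus reading would mix together. It does not describe a stated plan.

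**The analyses are descriptive.** Section 10.4.4 says so, the safety endpoints are counts and proportions, and the hypotheses and sample size concern efficacy only. A reader might conclude that a confirmatory safety claim is at risk. None is made. But the same section orders hypothesis tests, and their p-values will be read.

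**Every safety test is by preferred term.** A reader might infer this too. The Grade 3 comparison is on subjects with any such reaction, and overall percentages are tabulated as well.

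**Detail belongs in the statistical analysis plan.** Section 10.1 leaves methods and adjusted analyses to that plan, which may name pairs or add a pooled table, and nothing in 10.4.4 forbids it. That limits the weight of the point. Yet the protocol itself fixes the test and the study group as its unit, and naming only 1 v 4 and 2 v 5 would still leave 164 or 128 per arm.

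**Analysis by stratum is coherent.** The trial's premise is that baseline infection alters the response to the vaccine, and efficacy is analysed by stratum. This is a good reason to keep by-group tables. It does not justify leaving the vaccine contrast out.

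**Pooling does not rescue rare events.** This stands. For 1% v 0%, pooled power is 7.5%.

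**Conclusion.** The point holds as a cheap and worthwhile improvement. Section 10.4.4 orders tests between groups without saying which, and it omits the one contrast that uses all the randomised evidence on RTS,S against rabies: 292 v 292 in place of 164 v 164 or 128 v 128. At assumed rates of 3% to 6% on RTS,S, pooling raises power from 19-45% to 65-87%. At 1% to 2% it rises from 0.2-5.6% to 7.5-22%, so very rare terms remain underpowered.

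The consequence is lost sensitivity and p-values that are hard to interpret, within analyses that the protocol calls descriptive.

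Three limits apply. The event rates are assumptions. The 292 per arm is the number enrolled, and the safety population requires at least one vaccination, so it may be slightly smaller. The contrast is possible only where both vaccines are observed: section 7.1.1 states that solicited AEs are not captured in Groups 4 and 5, so no RTS,S v rabies test of solicited events, including solicited Grade 3 reactions, can be made.

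**What to change.** In section 10.4.4, and then in the statistical analysis plan:

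- Name RTS,S (Groups 1+2) v rabies (Groups 4+5), stratified by baseline parasitaemia, as the tested safety comparison. Use an exact Cochran-Mantel-Haenszel test, and report the stratified risk difference with its confidence interval.
- Apply it to any SAE, to adverse events of special interest as one grouped category, and to unsolicited AEs.
- Keep the by-group tables with exact confidence intervals as description, without tests between groups.
- Report Group 3 and all solicited AEs without RTS,S v rabies tests.
- Read the unsolicited comparison with some care. The trial is open label, and Appendix B limits the field visits 7 days after doses 2 and 3 to the reactogenicity cohort, which includes 50 + 50 = 100 of the 292 RTS,S subjects and no rabies subjects. The single-stratum pairs have the same limitation.

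The cost is a few sentences and one further table set, with no new data, visits or subjects, and fewer tests than an all-pairs reading would imply. The downside is that an effect confined to one stratum is diluted in the pooled estimate. It stays visible in the by-group tables.
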